Participants will be asked to record their pain intensity, 24- hour VAS and current VAS, before the procedure to establish a baseline pain score. Other data will be collected for secondary measures: frequency of pain attacks, basal and breakthrough opioid and non-opioid analgesic frequency and dose. Overall quality of life (PROMIS Global-10 short form) will be assessed.³⁹ Women of childbearing potential will undergo a urine pregnancy test prior to receiving the nerve block.

First trigeminal nerve block procedure: Participant will receive either study drug (guanfacine and lidocaine combination) or active control (lidocaine alone) for the trigeminal nerve block based on randomization. Participants will be monitored for pain intensity at 30-minute time intervals for the first 8 hours after block in addition to safety monitoring procedures. Participant responses will be collected at 30 minute intervals for the first 8 hours while in the recovery (first 60 minutes) and after discharge home, with responses allowed all the way until the next time point and actual time of the response being used in analysis. Assessments will be recorded according to the patient's preference, either on paper or via text message) using the Twilio application linked to REDCap. Patients will also receive a sheet with contact information for the study nurse.

First follow-up period (Day 2 to Day 14)

Participants will be monitored once daily at approximately the same timepoint for 14 days using text message generated using the Twilio application or recorded on a paper diary. Participants will also be monitored for any use of rescue medication (analgesics) once daily. The study nurse will monitor participants once weekly for overall quality of life via phone call using the PROMIS global 10 SF. Participants will be instructed to contact the study nurse with any adverse events directly by phone.

At the end of the first follow-up period, participants will be contacted for crossover to the other arm to receive the second trigeminal nerve block using the alternative drug (study drug or active control), not received during the first nerve block. At the second study visit, participants will record 24-hour VAS and current VAS, and the PROMIS Global-10 Short Form to establish baseline measurement again. Women of childbearing potential will undergo a urine pregnancy test prior to receiving the nerve block.

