9.0 STATISTICAL CONSIDERATIONS

The effects of guanfacine adjuvant (intervention) versus active control on the time to return to baseline pain (primary) will be assessed using linear mixed-effects regression, adjusting for randomization order group and its interaction with the intervention/control indicator. A random intercept indexed by study participant will be used to account for within-participant correlation of the pre- and post-crossover measurements. The linear model assumptions will be assessed by examining residuals, conditional on the empirical Bayes estimates of random effects. If there is evidence that the linear model assumptions are violated (e.g., non-normal residuals or the very unlikely possibility of right censoring), alternative model formulations will be considered as necessary. The overall effect of intervention on the primary outcome will be tested using a two degree-of-freedom chunk test against the null hypothesis of no intervention main effect and no order-by-intervention interaction. The effects of intervention on the mean time to return to baseline will be summarized using estimates and 95% confidence intervals, stratified by order group. The effects of guanfacine adjuvant versus active control on secondary outcomes will be assessed using similar mixed-effects regression techniques as appropriate for the type of outcome (including proportional hazards, cumulative logit, logistic, and linear regression methods), adjusting for

randomization order group and its interaction with the intervention/control indicator. A random intercept indexed by study participant will be used to account for within-participant correlation. Quantitative and/or graphical regression diagnostics will be examined, and alternative model formulations will be considered as appropriate. Intervention effects will be tested and summarized as described above. No familywise hypotheses will be tested; no adjustments will be made to control any familywise type-I error probability. The type-I error rate will be fixed at 5%. All statistical analyses will be implemented in R (www.r-project.org; latest version) and the add-on package "lme4" and other packages as necessary.

9.1 Statistical power and sample size. Evidence from the medical literature and expert opinion suggests that the mean duration of pain relief after treatment with lidocaine alone (active control group) is approximately 140

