minutes. The sample size for the proposed study was selected to achieve at least 80% power to detect a 20% or greater increase in the duration of pain relief after treatment with lidocaine plus guanfacine as an adjuvant (treatment group). This corresponds to a mean difference of 28 minutes. Again, although this degree of difference is not likely to be clinically meaningful, we are conducting this trial as a proof of mechanism only. If successful, we would pursue a modified formulation of guanfacine such that delivery was extended and pain relief duration was considerably longer. A simulationbased power analysis was implemented using linear mixed-effects regression as described above. Both betweenand within-subjects variability conservatively assumed to have standard deviation 30

minutes. Under these conditions, 30 participants will ensure approximately 90% power to detect a significant mean difference (28 minutes or greater in pain relief duration). **Figure 2** illustrates the estimated statistical power for somewhat larger and smaller effect sizes (i.e., 15%, 20%, and 25% increase in pain relief duration), for a variety of sample sizes.

Dropout and intent-to-treat: If VAS < 5 on the pain scale, participants will not be eligible for second trigeminal nerve block during the visit. Study nurse will continue monitoring the participant's pain intensity daily (days 15-28) to monitor when the participant pain is above 5 on the pain scale and eligible for the second block. In general, the study intends that participants would receive both treatments unless they experience intolerable toxicity. If a participant is unable or ineligible to receive second trigeminal nerve block, then the participant's data collected during the first nerve block will be included in the final analysis. In addition, a replacement participant will be enrolled so that the minimum number of 30 for each arm is reached. An exploratory analysis will be done post-hoc to evaluate any differential progress to second block between the initial randomized groups. Approximately 70 people with painful trigeminal neuropathy will be evaluated at Vanderbilt University Medical Center to determine if they are eligible to take part in this study. We expect to consent 70 subjects with 30 completing the full study.

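### The secondary-outcome models leave out the pre-block values already recorded in each period, giving up precision in the guanfacine contrast if pre- and post-block values are related within a participant

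*Combined protocol and SAP*

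**What the plan says.** Section 2.0 (Endpoints) defines three of the secondary outcomes as what is observed after each block: VAS pain intensity, PROMIS Global-10 and frequency of pain attacks. Only the primary endpoint, time to return to baseline pain, refers to a baseline.

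Section 9.0 says that the effects "on secondary outcomes will be assessed using similar mixed-effects regression techniques as appropriate for the type of outcome", adjusting for "randomization order group and its interaction with the intervention/control indicator". It adds: "A random intercept indexed by study participant will be used to account for within-participant correlation". It names no pre-block covariate and no change-from-baseline response. Testing and reporting follow the primary: "Intervention effects will be tested and summarized as described above". That means a "two degree-of-freedom chunk test against the null hypothesis of no intervention main effect and no order-by-intervention interaction", with effects "summarized using estimates and 95% confidence intervals, stratified by order group".

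The pre-block values exist. In Section 5.0, VAS and PROMIS are taken before the first block. Before the second block, participants give VAS again and "the PROMIS Global-10 Short Form to establish baseline measurement again". For attack frequency, the text names a value at the first procedure visit. The value at the second rests on the schedule table alone, which does not say that it is taken before the block.

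The blocks are at least 15 days apart. If VAS is too low, monitoring continues "to monitor when the participant pain is above 5 on the pain scale and eligible for the second block" (Section 9.1). Participants who never receive a second block stay in the analysis.

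**The concern.** A crossover gains its precision by comparing each participant with himself or herself. Whatever differs between a participant's two periods for reasons other than treatment becomes noise in that comparison. The starting level is one such thing. A participant may enter the first block at VAS 9 and the second at VAS 6, since the second block depends on a pain threshold and not on return to the first starting level. PROMIS and attack frequency have no entry threshold at all.

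The trial measures this source of noise and then does not use it. At stake is the width of the intervals for VAS, PROMIS and possibly attack frequency. There is also some protection to be had if starting levels at block 2 happen to differ between the two orders.

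**Working it through.** **The plan's own figure.** The documents give power only for the primary outcome: about 90% with 30 participants, a 28-minute difference and within-participant SD 30. The noncentrality is n·δ²/(2·SD²) = 30·28²/(2·30²) = 23,520/1,800 = 13.07. The 2-df chi-square power is then 0.909, so the stated figure reproduces. The present point does not affect it.

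**What the planned terms remove.**
- The random intercept removes a participant's stable level.
- In a 2x2 crossover, order-by-intervention is aliased with period. A shift common to both orders therefore cancels from the average of the two order-specific estimates (simulated bias about 0).
- What remains is the participant-specific change in starting level, which no planned term captures.

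**Inputs for precision.** 30 completers, 15 per order (Sections 2.0 and 5.0). The within-participant correlation r of pre- and post-block values is not in the documents; it is assumed at 0, 0.3, 0.5 and 0.7. Units are within-participant SDs.

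**Formula.** Regress each participant's period difference on order, with and without the pre-block difference. For a normally distributed covariate, the ratio of the variances of the treatment contrast (adjusted/unadjusted) is (1 - r²)·(1 + 1/(n - 4)), here (1 - r²)·(1 + 1/26) = (1 - r²)·1.038.

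| r | Formula | Simulated | Change in variance |
|---|---|---|---|
| 0 | 1.000·1.038 = 1.04 | 1.04 | +4% |
| 0.3 | 0.910·1.038 = 0.94 | 0.95 | about -5% |
| 0.5 | 0.750·1.038 = 0.78 | 0.75 to 0.78 | -22 to -25% |
| 0.7 | 0.510·1.038 = 0.53 | 0.54 to 0.55 | -45 to -47% |

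Interval width goes with the square root: √0.78 = 0.88 at r = 0.5 and √0.53 = 0.73 at r = 0.7. The order-specific estimates that the plan reports gain in the same way. With no shift, the simulated standard error for one order falls from 0.367 to 0.331 at r = 0.5 and from 0.360 to 0.267 at r = 0.7.

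**If starting levels differed by order.** Suppose only the guanfacine-first group enters block 2 one unit (one SD) lower. The bias in the order-averaged contrast depends on how much of that shift reaches the post-block level:

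| Pass-through of the shift | Planned model, r = 0.3 / 0.5 / 0.7 | With pre-block value |
|---|---|---|
| Full | 0.50 / 0.50 / 0.50 | 0.35 / 0.25 / 0.15 |
| In proportion to r | 0.15 / 0.25 / 0.35 | about 0 |

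The full-pass-through row is 0.50 before adjustment and 0.50·(1 - r) after it. The proportional row is 0.50·r before adjustment.

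**The cost in that case.** A shift that differs by order makes the covariate partly collinear with treatment. This adds [1²/(2·26)]/(2/15) = 0.0192/0.1333 = 0.144 inside the second bracket. At r = 0.3 the ratio becomes 0.91·(1 + 0.038 + 0.144) = 1.08. Variance then rises by about 7 to 8%, where without the shift it fell by 5%.

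**The case against.** **The gain may be small.** For r up to 0.3 the variance changes by only +4% to -5%, and the documents give no r. That stands. The gain becomes material at r of about 0.5 or more.

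**Bias against guanfacine is not shown.** A reader might infer that drift between periods is built into the design, and that guanfacine-first participants will start block 2 lower if the drug works. The documents support neither. Both blocks require pain above essentially the same VAS threshold, so nothing points to a systematic shift. The planned gain is 28 minutes on about 140 (Section 9.1), the stated half-life is about 17 hours (Section 1.0), and the gap is at least 15 days: 15·24/17 = about 21 half-lives. The one-unit shift is purely an assumption, and 0.50 is its size only under full pass-through. This objection stands.

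**Drift does not all go into the error.** Also correct: average drift is absorbed by the interaction term. It does reach the order-stratified estimates and the 2-df test. With a 0.5 SD shift in both orders and no treatment effect, that test rejects 7.6%, 11.8% and 18.8% of the time at r = 0.3, 0.5 and 0.7, against about 5% after adjustment. But this follows from testing period jointly with treatment, which is a separate matter.

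**The covariate is not a clean baseline.** The second pre-block value comes after randomization and could carry a first-block effect. That justifies a sensitivity analysis. It does not justify ignoring the value.

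**The plan leaves room.** Section 9.0 allows alternative formulations, but in connection with regression diagnostics. That does not prespecify this covariate, and choosing it after seeing the data would be open to question.

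**Conclusion.** The concern holds as a missed gain in precision. The planned models for post-block VAS, PROMIS Global-10 and attack frequency leave participant-specific change in starting level in the error, although the trial records the values needed to remove it. With 30 completers the effect on variance runs from about +4% (r = 0) to about -45% (r = 0.7). It rests on an assumed r and on a completers-only calculation. Some protection against bias comes with it if starting levels at block 2 happen to differ by order, but the documents do not show that such a difference is expected, so the point should not be read as a finding of bias. For attack frequency it is conditional on the second-visit value being taken before the block. The primary analysis, the sample size and the stated power are untouched. In a pilot with no familywise claims this is a modest improvement, but a nearly free one.

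**What to change.** In Section 9.0:

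1. For VAS and PROMIS Global-10, prespecify the same measure's period-specific pre-block value as a covariate. For VAS, state whether the current or the 24-hour score is used.
2. Do the same for attack frequency once Section 5.0 confirms that the second-visit value is taken before the block.
3. Enter it as two terms: the participant's mean of the available pre-block values, and the period's deviation from that mean. This keeps between-participant differences out of the within-participant comparison.
4. For participants with one block, set the mean to the single value and the deviation to 0, so that they stay in the analysis as planned.
5. Report the model without the covariate as a sensitivity analysis, because the second pre-block value is post-randomization.

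**Cost:** a short paragraph of plan text, one or two degrees of freedom and no new data. If pre- and post-block values are unrelated within a participant, variance rises by about 4%, and by more if starting levels also differ by order.

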10.0 PRIVACY/CONFIDENTIALITY ISSUES

A database will be designed for this study using REDCap (Research Electronic Data Capture) tools. REDCap is a secure, web-based application designed to support data capture for research studies and was developed specifically around HIPAA-Security guidelines. PI and study personnel are trained in HIPAA privacy regulations. All reasonable efforts will be made to keep a patient's protected health information (PHI) private and confidential. Participants will be identified with a study identification number. There will be limited access to medical records and de-identification of all records. Federal privacy guidelines will be followed when using or sharing any protected health information.

Much like email, text messaging is not considered a secure form of communication. These surveys use a third-party service called Twilio to deliver the text messages and collect your answers. REDCap goes to great lengths to ensure that text transcripts do not stay in Twilio's records but are removed shortly after being completed and transferred to REDCap. This is done for privacy and security concerns—answers and phone number do not get permanently logged in Twilio's computers but instead remain securely in REDCap.


APPENDIX A: FORMULATION INSTRUCTIONS FOR GUANFACINE 250 MCG IN LIDOCAINE 1% PF 6 ML FOR INJECTION (GUANFACINE HYDROCHLORIDE AND LIDOCAINE 1%, INJECTION)

Final Product: Guanfacine hydrochloride 250 mcg in lidocaine 1% PF 6 mL

Final Concentration: 41.67 mcg/mL

Supplied: Guanfacine hydrochloride powder (Procos S.p.A.)

Storage: 72 hours refrigerated

Dispensing: Dispense in a 10 mL syringe with tamper evident leur cap

Supplies: Guanfacine hydrochloride powder

Lidocaine 1% PF 30 mL vial

Weight boat

5 mL, 10 mL, and 60 mL sterile syringes

0.22 micron disk filter

MIXING INSTRUCTIONS:

- 1. Compounding area is clean, sanitized, and free of components and/or residue of other compounding procedures and the compounder is wearing appropriate PPE.
- 2. Tare weight boat and print. Weigh 0.03 g of guanfacine hydrochloride powder and print.
- 3. Draw up 24 mL Sterile Water (SWFI) and add to weighted guanfacine hydrochloride powder to make aliquot (30,000 mcg/24 mL).
- 4. Draw up 1 mL of guanfacine aliquot (1250 mcg/mL).
- 5. Draw up 29 mL of Lidocaine 1%.
- 6. Allow pharmacist(s) to check ingredients (compounding verification)
- 7. Pull plunger from a 60 mL syringe and add a tip cap.
- 8. Add 29 mL of Lidocaine 1% to barrel.
- 9. Add 1 mL of guanfacine aliquot (1250 mcg/mL) to barrel.
- 10. Replace plunger and attach a 0.22 micron disc filter and leur to leur adapter to filter 6 mL of solution into the final 10 mL syringe.
- 11. Add a tamper evident leur cap.
- 12. Perform filter integrity test and bubble test on the filter.
- 13. Filter integrity test PSI Bubble Test PSI (PASS/FAIL)
 - a. The minimum bubble point is 46 psi for this filter unit. Presence of bubbles at less than 46 psi represents a filter failure and the compounding process must be aborted.
 - b. A successful bubble point test coupled with the satisfactory testing results (sterile per USP<71>) on the representative process verification sample performed prior to opening the study serve as criteria for release of the dose.
- 14. The compounding area is clean and sanitized and free of components and/or residue of this preparation.
- 15. Final verification and quality assurance check by:

Pharmacist:				Date:		Time:	
			_				

- a. Rx Label syringe with a 72 hour expiration refrigerated per USP 797.
- b. The compounded preparation label has been affixed to the final container
- c. High alert sticker has been affixed to final container
- d. "Medication is sterile, Packaging is not" has been affixed to the final container
- e. No particles observed
- f. Final weight and volume of preparation has been verified
- g. Preparation dispensed in an appropriate container
- h. Container is not contaminated by drug

FORMULATION INSTRUCTIONS FOR LIDOCAINE 1% PF 6 ML FOR INJECTION (LIDOCAINE 1%, INJECTION)

Final Product: Lidocaine 1% PF 6 mL

Supplied: n/a

Storage: 72 hours refrigerated

Dispensing: Dispense in a 10 mL syringe with tamper evident leur cap

Supplies: Lidocaine 1% PF 30 mL vial

10 mL and 30 mL sterile syringes

0.22 micron disk filter

MIXING INSTRUCTIONS:

- 1. Compounding area is clean, sanitized, and free of components and/or residue of other compounding procedures and the compounder is wearing appropriate PPE.
- 2. Draw up 10 mL of Lidocaine 1%.
- 3. Allow pharmacist(s) to check ingredients (compounding verification)
- 4. Add Lidocaine 1% to a clean 30 mL syringe.
- 5. Attach a 0.22 micron disc filter and leur to leur adapter to filter 6 mL of solution into the final 10 mL syringe.
- 6. Add a tamper evident leur cap.
- 7. Perform filter integrity test and bubble test on the filter.
- 8. Filter integrity test PSI Bubble Test PSI (PASS/FAIL)
 - a. The minimum bubble point is 46 psi for this filter unit. Presence of bubbles at less than 46 psi represents a filter failure and the compounding process must be aborted.
 - b. A successful bubble point test coupled with the satisfactory testing results (sterile per USP<71>) on the representative process verification sample performed prior to opening the study serve as criteria for release of the dose.
- 9. The compounding area is clean and sanitized and free of components and/or residue of this preparation.
- 10. Final verification and quality assurance check by:

Pharmacist:	Date:	Time:
-------------	-------	-------

- a. Rx Label syringe with a 72 hour expiration refrigerated per USP 797.
- b. The compounded preparation label has been affixed to the final container
- c. High alert sticker has been affixed to final container
- d. "Medication is sterile, Packaging is not" has been affixed to the final container
- e. No particles observed
- f. Final weight and volume of preparation has been verified
- g. Preparation dispensed in an appropriate container
- h. Container is not contaminated by drug
